## LIST OF ABBREVIATIONS

*Add all other abbreviations referenced in the protocol and delete any not referenced in the protocol.*

AE	adverse event
CFR	Code of Federal Regulations
CRF	case report form
DSMB	Data Safety Monitoring Board
FDA	Food and Drug Administration
GCP	Good Clinical Practice
HIPAA	Health Insurance Portability and Accountability Act of 1996
HIV	Human immunodeficiency virus
ICF	informed consent form
IRB	Institutional Review Board
PI	Principal Investigator
PK	Pharmacokinetic
POC	Point-of-care
SAE	serious adverse experience
SOC	Standard-of-care
TAF	tenofovir alafenamide
TDF	tenofovir disoproxil fumarate
TFV	Tenofovir
TFV-DP	Tenofovir-diphosphate
YMSM	young men who have sex with men

**PROTOCOL SYNOPSIS**

TITLE	PREP POINT-OF-CARE BRIEF-INTERVENTION FOR ADHERENCE AMONG YOUNG MSM (PREP2-BAY)
PI	[name], MAS
FUNDING ORGANIZATION	U.S. National Institute of Mental Health
NUMBER OF SITES	Study procedures performed remotely (over video chat) at University of California, San Francisco and University of Miami
RATIONALE	
Young men who have sex with men (YMSM; ages 18-30 years) have rising HIV incidence in the United States. Pre-exposure prophylaxis (PrEP) is a highly effective medication prevent HIV infection, both at the individual and population level. However, in several clinical trials and demonstration projects among YMSM, a majority of participants had adherence to PrEP sufficiently low to compromise efficacy throughout the study. Unfortunately, pill-counts and self-reported adherence have limitations in this population, and therapeutic drug monitoring using previously available methods requires expensive equipment and specialized staff, meaning it cannot be implemented at the point-of-care (POC). We have developed a novel POC test to measure urine drug-levels to PrEP for the first time, providing the opportunity to target and enhance adherence counseling during a routine clinical visit. Substantial knowledge gaps on the correct counseling approach and framing of the drug-level feedback message must be addressed to use this strategy to improve adherence among YMSM. This study will use a mixed methods approach to test the central hypothesis that an intervention leveraging a POC urine bioassay to detect PrEP adherence can both target and enhance adherence counseling. Brief interventions are a motivational interviewing (MI) counseling approach with wide uptake by primary care providers for substance use prevention and medical therapy adherence. PrEP2-BAY proposes a brief intervention be used as the framework for POC drug-level feedback among YMSM using PrEP. This study will test the acceptability and preliminary impact on long-term adherence, measured through hair tenofovir levels, of the brief intervention in a pilot randomized controlled trial among YMSM. This proposed research plan has the goal of optimizing PrEP's impact through a novel adherence support intervention. The findings of this proposal will lead to a R01 application to test a POC bioassay-enhanced adherence brief intervention among YMSM in a multi-city trial, with the goal of reducing the burden of HIV among MSM.

STUDY DESIGN	This is a randomized, unblinded, open-label pilot study

PRIMARY OBJECTIVE	To test the acceptability to participants and impact on a longer-term metric of adherence among participants (assessed via tenofovir levels in hair) of implementing POC urine tenofovir testing and providing adherence feedback and motivational interview-based counseling among YMSM in the U.S.
NUMBER OF SUBJECTS	60 participants, 40 in the intervention arm and 20 in the standard-of-care arm
SUBJECT SELECTION CRITERIA	
Inclusion Criteria:
 
 
1. Age 18-30 years.
 
2. Primary sexual partners are male sex at birth
 
3. Able to understand, read, and speak English.
 
4. Currently taking TDF/FTC-based, daily PrEP and planning to continue for at least 3 months
 
5. Willing to provide a hair sample
 
 
Exclusion Criteria:
 
 
1. Any health condition that may interfere with participation or the ability to provide informed consent, including any debilitating or life-threatening conditions
 
2. Currently enrolled in another HIV intervention study.
 
3. Known to be HIV-infected.
 

POC TESTING	Urine tenofovir testing by lateral flow assay performed at each of 2 counseling sessions approximately 2-3 months apart
CONTROL	Participants will continue to receive standard of care at their PrEP clinic without the PrEP2-BAY adherence counseling intervention
DURATION OF SUBJECT PARTICIPATION AND DURATION OF STUDY	Participants will be enrolled in the study for a maximum of 3 months, including the enrollment period and 3 months of study follow-up.
PRIMARY ENDPOINT	
 
• Acceptability: Number of participants indicating satisfied or very satisfied with the intervention
 
• Description: Number of participants reporting to be "satisfied" or "very satisfied" about their overall experience on a five-point Likert scale.
 
• Time Frame: 3 months
 

SECONDARY ENDPOINTS	
 
• Change in tenofovir levels in hair from baseline and after 3 months of follow-up
 

PLANNED INTERIM ANALYSES	When approximately 50% of patients have completed all study procedures, an interim analysis of all data will be conducted by an

	independent DSMB. Serious adverse events will be monitored by the committee on an ongoing basis throughout the study.
STATISTICS Primary Analysis Plan	
Acceptability will be the primary outcome for this pilot randomized controlled trial, and will be assessed via tabulation of survey results with graded answers in the intervention arm. Frequency distributions of the Likert scale will be summarized. Advantages and disadvantages of the bioassay enhanced brief adherence intervention will be tabulated, including manually reviewing and assigning open-ended responses under the “other” option to appropriate pre-specified categories. We will use a threshold of <math>\geq 75\%</math> reporting that they were at least somewhat satisfied with the full PrEP2-BAY intervention.
 
After analysis of the quantitative results, we will explore mechanisms of acceptability using a sequential explanatory mixed methods approach. Qualitative interviews from the participants and providers will be performed, a debrief report will be prepared, and audio recordings will be professionally transcribed. Coding and analysis will be performed in the Dedoose cloud-based analysis platform to facilitate collaboration and comparison of coding transcripts. At least 10% of transcripts will be double-coded and compared among the analytic team and inter-coder agreement will be calculated. Inconsistent results will be reviewed by coders until consensus on codes and themes is reached.
 
Preliminary impact on adherence as assessed by hair tenofovir levels (long-term adherence): The first adherence analysis will include use of a mixed effects logistic regression model to estimate the effect of the intervention vs. SoC arm on optimal vs. sub-optimal adherence (<math>< 700</math> fmol/punch) equivalent to at least 4-times weekly average dosing over the prior three months. We will include a random intercept term to account for within-person correlation over two timepoints; and time points will be included as a categorical variable to account for systematic changes over time. We will also analyze continuous tenofovir-diphosphate levels between intervention and SoC arms using a censored-mixed effects linear regression with logarithmically transformed levels of tenofovir in hair.

Rationale for Number of Subjects	We will assess sample size based on the primary endpoint of acceptability, with a threshold of $\geq 75\%$ reporting that they were at least somewhat satisfied with the full PrEP2-BAY counseling intervention. We will base our estimate of acceptability on a similar intervention performed among Los Angeles MSM (PATH-PrEP),  which was $\sim > 90\%$ acceptable. Using an estimate of PrEP2-BAY being somewhat acceptable for 90% of the 40 individuals in the intervention

	arm, we would have 82% power to detect acceptability of 75% or less with a one-sided alpha of 0.015.
--	--

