## 1 BACKGROUND

**Adherence challenges in YMSM threaten to compromise PrEP's effectiveness.** Men who have sex with men (MSM) are the only risk group in the U.S. who have not experienced decreased HIV incidence, with increasing incidence specifically demonstrated among young MSM (YMSM). PrEP with adequate adherence is highly effective, both at the individual and population level. A recent analysis demonstrates that, among sexually active US MSM, the proportion eligible for PrEP has jumped from 24.7% in 2015 to 45% today with an update in practice guidelines. Indeed, rising numbers of U.S. MSM have initiated PrEP, with up to 50% of MSM having tried PrEP in the prior year in some districts, including San Francisco. PrEP expansion is a critical component of the newly-launched End the HIV Epidemic campaign in the U.S. However, poor adherence can compromise PrEP's effectiveness in the populations at greatest risk. Data from two U.S. PrEP demonstration projects has shown that up to 66-78% of YMSM exhibit low PrEP adherence. Furthermore, a drop-off in adherence may herald future PrEP discontinuation, meaning that new non-adherence may be a critical period for intervention in individuals who remain at risk. Although some stop PrEP due to decreasing HIV risk, many who stop PrEP remain at risk of HIV: in a Montreal clinic, the HIV incidence after stopping PrEP was as high as the placebo arm of the iPrEx trial.

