## 10.2 Statistical Analysis

Acceptability, the primary outcome, will be assessed through tabulation of survey results and in-depth interviews. We will use a threshold of  $\geq 75\%$  reporting that the full PrEP-BAY intervention was at least somewhat acceptable on a 5-point Likert scale, and then explore potential mechanisms through in-depth interviews using a sequential explanatory mixed methods approach. For the interviews, we will analyze transcripts using the codebook and theoretical model developed in Aim 2, applying it to a subset of transcripts. We will seek 90% agreement among coders prior to applying codes to the entire set of interviews. We will use code reports to organize findings into emergent themes and discuss these as a group and with the HIV prevention community advisory group.

Preliminary impact (adherence) will be assessed via a long-term adherence metric, namely DBS TFV-DP levels. We will use mixed effects logistic regression for high adherence (at least 4 times weekly dosing; TFV-DP  $\geq 700$  fmol/punch) comparing the interaction of adherence by intervention arm with time. Random intercepts will accommodate paired adherence levels. As an additional adherence outcome, we will examine continuous DBS TFV-DP levels using censored mixed-effects linear regression in a similar fashion.

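### The section 10.2 binary adherence model can be unstable with 20 controls, its odds ratio is person-specific rather than a population effect, and no population-level summary or fallback is planned

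*Combined protocol and SAP*

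**What the plan says.** The synopsis (Statistics, Primary Analysis Plan) puts the binary analysis first among the adherence analyses: "use of a mixed effects logistic regression model to estimate the effect of the intervention vs. SoC arm on optimal vs. sub-optimal adherence". The correlation between a person's two results is handled by a random intercept. On time, the synopsis says "time points will be included as a categorical variable to account for systematic changes over time". It mentions no arm-by-time term.

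Section 10.2 describes a different model, "comparing the interaction of adherence by intervention arm with time", and adds "Random intercepts will accommodate paired adherence levels".

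The sample is "60 participants, 40 in the intervention arm and 20 in the standard-of-care arm". Neither section gives an expected adherence proportion, a within-person correlation, an effect size, a test, a rule for a fit that does not converge, or a population-level measure such as a risk difference. A continuous censored mixed model is also planned. Acceptability is the primary outcome and adherence the secondary objective (section 3.2). Of later use, the synopsis says "The findings of this proposal will lead to a R01 application".

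**The concern.** With two binary results per person, the arm-by-time coefficient of a random-intercept logistic model is informed mainly by people who change category, and a 20-person control arm may contain few of them. The estimated random-intercept SD can then run off to very large values and take the odds ratio with it.

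When the fit behaves, the coefficient compares the odds for a given person under the two arms. That is a legitimate quantity, but it lies further from 1 than the odds ratio formed from the proportions adherent in each arm. The gap widens as within-person correlation rises.

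This is the first-listed adherence analysis of the trial's randomised comparison. A modest difference in the proportion adherent could be reported as a very large odds ratio, or the model could give no usable answer with nothing prespecified to replace it.

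**Working it through.** **Plan's own figure.** There is none to reproduce. The only power statement concerns acceptability.

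**Inputs from the documents.** 40 vs 20 participants, two timepoints, random intercept, with the interaction (section 10.2) or without a stated one (synopsis).

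**Assumptions.** Within-person correlation r between the two binary results is 0.3 to 0.6. Baseline adherence equals control adherence at month 3. Prevalence is varied because the documents point both ways. Section 1 cites "up to 66-78% of YMSM exhibit low PrEP adherence", which implies 22-34% adherent. Section 6.2 enrols current daily PrEP users who plan to continue, which makes near-ceiling adherence plausible.

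**Step 1: population vs person-specific odds ratio.** For 70 vs 85%, the population OR is (0.85/0.15)/(0.70/0.30) = 2.43. For the person-specific OR, choose the random-intercept SD so that the two binary results correlate at r. Then solve for the intercepts that give 70% and 85% after averaging over the random effect. The difference between these intercepts is the conditional log OR. With equal baselines, it is also the arm-by-time coefficient.

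| Control vs intervention, month 3 | Population OR | Person-specific OR at r = 0.3 / 0.4 / 0.5 / 0.6 | Ratio |
|---|---|---|---|
| 70 vs 85% | 2.43 | 3.4 / 4.1 / 5.5 / 8.4 | 1.4 / 1.7 / 2.3 / 3.5 |
| 85 vs 95% | 3.35 | 5.1 / 6.5 / 9.4 / 16.3 | 1.5 / 1.9 / 2.8 / 4.9 |
| 30 vs 45% | 1.91 | 5.2 (at r = 0.6) | 2.7 |

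**Step 2: stability of the section 10.2 model.** Trials of 40 vs 20 were simulated from these settings and refitted by maximum likelihood with numerical integration. Ranges cover separate runs of 120 to 400 trials per setting. A fit counts as degenerate when its random-intercept SD exceeds 10 or, in some runs, when the absolute log OR exceeds 5.

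- Away from the ceiling, r = 0.3-0.5: roughly 0-9% degenerate.
- Away from the ceiling, r = 0.6: roughly 8-14%.
- 85 vs 95%, r = 0.3-0.6: SD above 10 in roughly 8-47%.
- With 15% dropout (17 vs 34), 70 vs 85% and r = 0.5: about 12%, using absolute log OR above 5 or SD above 15.

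**Step 3: the synopsis model (arm + time).** Randomisation makes the arms alike at baseline, so one arm coefficient for both timepoints averages a null difference with the month-3 difference. At 50 vs 70% and r = 0.3, the median fitted arm OR was 1.7 against a true month-3 conditional OR of 3.3. On the log scale, 0.53/1.19 = 0.44, a little under half. At r = 0.6, across the three table settings, median arm ORs were about 2.1 to 4.0, against population ORs of 1.9 to 3.4.

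**Step 4: tests at r = 0.6** (70 vs 85%, 85 vs 95%, 30 vs 45%).

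| Method | Power |
|---|---|
| Wald test, interaction | 11%, 1%, 12% |
| Likelihood-ratio test, interaction | 32%, 32%, 27% |
| Month-3 risk difference adjusted for baseline | 30%, 16%, 30% |

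Under the null, the Wald test rejected in about 0.7% of trials (nominal 5%).

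**Step 5: precision of the risk difference.** The unadjusted 95% half-width is 1.96 × √[p0(1−p0)/20 + p1(1−p1)/40].

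- 50 vs 70%: 1.96 × √(0.0125 + 0.00525) = 0.26
- 70 vs 85%: 1.96 × √(0.0105 + 0.0031875) = 0.23
- 80 vs 95%: 1.96 × √(0.008 + 0.0011875) = 0.19

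The unadjusted risk difference was computable in every simulated trial and approximately unbiased. The baseline-adjusted version with HC3 standard errors had 92-96% interval coverage and 4.2-4.6% null rejection.

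**The case against.** A conditional odds ratio is a valid estimand, and the mixed model keeps people who return only one hair sample. That matters because hair is self-collected and mailed (section 9.2). Both points stand. The fitted model can also be rescued: averaging it over its random effect gave month-3 risk differences of 0.14-0.15 for a true 0.15 and 0.09-0.11 for a true 0.10, with similar spread in degenerate fits. Replacing the model is therefore not the only remedy.

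A reader might infer more than the documents support:

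- **That the model is often not estimable.** This needs high correlation or near-ceiling adherence, and the documents establish neither. The chance that no control changes in one direction is 2(1−d)^20 − (1−2d)^20, where d is the probability of change in each direction. It equals 59.5% for d = 0.05 and 23.2% for d = 0.10. These are not failure rates, because between-person information also contributes. At r = 0.6 such trials had SD above 10 in only 45% (70 vs 85%) and 37% (30 vs 45%).
- **That the synopsis odds ratio is several times too large.** It is not. That model's fault is dilution.
- **That the test will have almost no power.** This is true of a Wald test, but the plan names no test, and a likelihood-ratio test recovers the power.
- **That the R01 will be missized.** The documents link the findings to the application but do not say this odds ratio will size it. Acceptability and the continuous hair analysis will also inform it.

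**Conclusion.** The concern holds in a conditional form. The section 10.2 model can be fragile at 40 vs 20, and its odds ratio should not be read as a population effect. At moderate correlation away from the ceiling the discrepancy is limited. It becomes large at r = 0.6 or near the ceiling, and greater still at r = 0.7 (a conditional OR of about 17 against 2.43 for 70 vs 85%).

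All sizes rest on assumed correlation, prevalence and effect. The plan cannot know in advance which setting it will meet, so it should prespecify an effect measure that can be read in all of them. What can be established from the text alone is that the two sections describe different models, that the synopsis model does not target the month-3 effect, and that neither section provides a population-level summary or a fallback.

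**What to change.** - State one binary adherence model, identically, in the synopsis and section 10.2.
- Make the reported binary effect the month-3 risk difference (intervention minus SoC) adjusted for baseline category, with a 95% CI. Use linear regression on the 0/1 outcome with HC3 standard errors, or logistic regression with standardisation. Alternatively, standardise the fitted arm-by-time mixed model over its random effect, which keeps people with one sample.
- If the mixed model is kept, test the interaction by likelihood ratio or re-randomisation rather than Wald. Define a degenerate fit in advance and name the risk difference as the fallback.
- State that the conditional odds ratio will not be used as a population effect in R01 planning.

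The change takes a few sentences and little programming, but it has statistical costs. The estimate is imprecise. A baseline-adjusted regression drops people missing a sample. Near the ceiling it may have less power than a likelihood-ratio test (16% vs 32% at 85 vs 95%, r = 0.6).

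Separately, the 700 fmol/punch cut-off belongs to TFV-DP in dried blood spots in section 10.2, whereas the specimen collected is hair. Those passages must be reconciled before any binary outcome is defined. The present point applies whatever cut-off results.

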#### 5.2 Secondary Endpoint

Preliminary impact on adherence as assessed by tenofovir hair levels (long-term adherence): Change in tenofovir levels in hair from baseline and after 3 months of follow-up will be compared between the intervention and standard of care arm.

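### The synopsis adherence model names no arm-by-time term; read with the usual arm coding, its arm effect is about half the month-3 effect and differs from the section 10.2 estimate

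*Combined protocol and SAP*

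**What the plan says.** The synopsis (Statistics, Primary Analysis Plan) describes a mixed-effects logistic model to "estimate the effect of the intervention vs. SoC arm on optimal vs. sub-optimal adherence". Visit enters only as a main effect in the wording given: "time points will be included as a categorical variable to account for systematic changes over time". The repeated samples from one person are linked by a random intercept over the two visits. The continuous analysis is described as "using a censored-mixed effects linear regression with logarithmically transformed levels of tenofovir in hair", with no time term mentioned. Neither description names an arm-by-time product or says how arm is coded at baseline.

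Section 10.2 describes a mixed-effects logistic model "comparing the interaction of adherence by intervention arm with time", again with a random intercept for the paired samples. The continuous analysis is to follow in a similar fashion.

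Section 5.2 defines the secondary endpoint as "Change in tenofovir levels in hair from baseline and after 3 months of follow-up", compared between arms. Section 9.2 places the two hair samples at enrollment and month 3. Randomization is at the screening/enrollment visit (section 9.1). The trial has "60 participants, 40 in the intervention arm and 20 in the standard-of-care arm".

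The outcome also differs. The synopsis refers to hair but applies a 700 fmol/punch cut-off, and it names tenofovir-diphosphate in the continuous analysis. Section 10.2 names tenofovir-diphosphate in dried blood spots. Sections 3.2 and 5.2 name hair.

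**The concern.** Arms are formed by randomization and the enrollment sample precedes any effect of counseling, so the expected arm difference at baseline is zero. A model with arm and time but no interaction forces one arm difference on both visits. Its arm coefficient is then a blend of zero and the month-3 effect. A larger sample does not remove this.

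The synopsis rationale says that the findings will lead to an application for a multi-city trial. If a halved effect were carried into that trial's sample size, the required number would be inflated by 1/0.5² = 4, or a useful intervention might look too weak to pursue. Two differently worded models also leave the choice open until the data are seen.

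**Working it through.** **Inputs from the documents.** 40 and 20 participants; two samples per person (enrollment, month 3); random intercept; randomization before any effect of counseling. The documents give no effect size, SD, within-person correlation or power for adherence, so there is no figure of the plan's own to reproduce.

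**Assumptions.** Month-3 effect δ = 0.8 SD; correlation ρ from 0.3 to 0.8; two-sided α = 0.05; baseline difference 0; c = 1/40 + 1/20 = 0.075.

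**Linear model, complete data (SD units):**

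| Model | Expected estimate | Variance |
|---|---|---|
| Arm + time (arm constant over time) | δ/2 | (1+ρ)c/2 |
| Arm-by-time interaction, free baseline | δ | 2(1−ρ)c |
| Baseline-adjusted or common baseline mean | δ | about (1−ρ²)c |

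At ρ = 0.5:

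- Arm + time: 0.40/√0.05625 = 1.69, power 39%.
- Interaction: 0.80/√0.075 = 2.92, power 83%.
- Baseline-adjusted: 0.80/√0.05625 = 3.37, power 92%.

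Over ρ = 0.3 to 0.8, power runs from 44% down to 34% (arm + time), from 70% up to 99.6% (interaction) and from 87% up to 99.8% (baseline-adjusted).

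**Simulation check** (60 participants, 400 runs, ρ = 0.5, true effect 0.80):

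| Month-3 dropout | Arm + time | Interaction | Common baseline |
|---|---|---|---|
| 0% | 0.399 | 0.788 | 0.792 |
| 20% | 0.343 | 0.809 | 0.809 |

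With 20% dropout the arm coefficient is 0.343/0.80 = 43% of the truth, because people with only a baseline sample pull it toward zero.

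**Logistic model**, the one to which the quoted time term belongs. Random-intercept fits at 600,000 participants (random-intercept SD 1 to 3, baseline log odds 0 or 0.85, true odds ratio 2 or 4) give an arm log odds ratio of 0.42 to 0.51 of the true month-3 value. A true odds ratio of 4 appears as 1.79 to 1.94. The interaction and common-baseline models recover 0.99 to 1.04 of the truth.

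**Precision of the section 10.2 model.** The variance ratio, interaction to baseline-adjusted, is 2(1−ρ)/(1−ρ²) = 2/(1+ρ):

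| ρ | 0.3 | 0.5 | 0.7 | 0.8 |
|---|---|---|---|---|
| Ratio | 1.54 | 1.33 | 1.18 | 1.11 |

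Baseline adjustment therefore saves (1−ρ)/2 of the interaction's variance, from 35% down to 10%. The logistic analogue is about 1.67, 1.17 and 1.21 at random-intercept SD 1, 2 and 3 (250 runs, approximate).

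**Same comparison at an effect for which baseline adjustment has 80% power** (z = 2.80):

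- Interaction z = 2.80/√(2/(1+ρ)). At ρ = 0.5 and 0.7 this is 2.42 and 2.58, power 68% and 73%.
- Arm + time z = 1.40·√(2(1−ρ)). At ρ = 0.5 and 0.7 this is 1.40 and 1.08, power 29% and 19%.

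**The case against.** A reader might infer that the plan has chosen a model that halves the effect. The documents do not go that far. The synopsis is silent on the interaction; it does not exclude it. If arm were coded zero for everyone at baseline, the same words would describe a sound common-baseline model. Section 10.2 names the interaction, section 5.2 compares change between arms, and section 4.1 describes a baseline to month 3 comparison across arms. The synopsis is abbreviated, and for the continuous analysis it states no time term at all, so arm plus time is only an inference there. All of this stands. What remains is that nothing says which description governs, and the synopsis sentence, followed with ordinary coding, gives a different and diluted estimate.

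A reader might also infer that section 10.2 is wrong. It is not. The interaction is unbiased for the declared endpoint, and its only weakness is lost precision, of a size that depends on an assumed correlation.

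A common baseline mean has its own risk. The trial is open-label, the schedule in section 9.2 puts randomization before the Month 0 hair sample, and that sample is self-collected and mailed. If its return depends on known assignment, the baseline means of those who send one may differ by arm. The free-baseline interaction tolerates stable differences of that kind and so deserves a place as a sensitivity analysis.

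**Conclusion.** The point holds as an inconsistency with a material consequence. Under a time-constant arm indicator, the synopsis model estimates about half the month-3 effect. Exactly half applies only to the linear model with complete data; the ranges above cover the logistic model and dropout. The estimate matches neither the endpoint in section 5.2 nor the model in section 10.2. The dilution does not depend on ρ in the complete-data linear case; the power and precision figures do depend on the assumed ρ and δ.

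It would be tempting to call this critical to the trial. The documents do not support that. Acceptability is the primary endpoint, the sample size rests on it, and it is untouched. Adherence appears in the synopsis's primary objective but is the secondary objective and endpoint in sections 3.2 and 5.2, and no power is claimed for it, so the power figures above contradict nothing in the plan. It should be fixed before analysis.

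**What to change.** State one model, in the same words, in the synopsis and section 10.2, with the month-3 arm contrast as its estimate.

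- **Preferred:** a censored mixed model on log level, with a random intercept, categorical time, a common baseline mean and an arm effect at month 3 only. It keeps participants with one sample.
- **Alternative:** month-3 log level (left-censored at the assay limit) on arm plus baseline log level. It drops participants missing either sample, so it is not interchangeable with the preferred model when samples are lost.
- **Report** the month-3 ratio of geometric means with its 95% confidence interval.
- **Sensitivity analysis:** the free-baseline arm-by-time interaction, for the reason given under the objection.
- **If the binary analysis is kept,** give it the same month-3 contrast.
- **Reconcile the outcome:** hair, the fmol/punch cut-off and dried-blood-spot tenofovir-diphosphate cannot all describe one measurement. Aligning the arm term alone would not make the two descriptions one analysis.

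The cost is wording only. Both hair samples are already planned.

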### 5 CRITERIA FOR EVALUATION

#### 5.1 Primary Endpoint

Acceptability will be the primary outcome for this pilot randomized controlled trial, and will be assessed via tabulation of survey results with graded answers in the intervention arm. We will use a threshold of  $\geq 75\%$  reporting that they were at least somewhat satisfied with the full PrEP2-BAY intervention. After analysis of the quantitative results, we will explore mechanisms of acceptability using a sequential explanatory mixed methods approach.

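### The stated 82% power at one-sided alpha 0.015 cannot be obtained with 40 intervention participants, whichever of 90% and 75% is the null

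*Combined protocol and SAP*

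**What the plan says.** The sample size is justified in one place, the synopsis entry Rationale for Number of Subjects. It rests on the primary endpoint, acceptability, "with a threshold of $\geq 75\%$ reporting that they were at least somewhat satisfied". The planning value comes from a similar intervention among Los Angeles MSM: "Using an estimate of PrEP2-BAY being somewhat acceptable for 90% of the 40 individuals in the intervention" arm. From this it concludes "we would have 82% power to detect acceptability of 75% or less with a one-sided alpha of 0.015".

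The synopsis confirms the arm sizes: "60 participants, 40 in the intervention arm and 20 in the standard-of-care arm". Section 5.1 says that acceptability "will be assessed via tabulation of survey results with graded answers in the intervention arm", judged against the 75% threshold. The synopsis analysis plan and Section 10.2 say much the same. None of these places names a hypothesis test, a cut-off count or a formula. Section 10.2 gives no power figure, and no allowance for missing surveys is stated.

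**The concern.** Four inputs fix the calculation: n = 40, 90%, 75% and alpha 0.015. With a single binomial proportion and only 40 people, the attainable alpha and power come in coarse steps, one pair per cut-off, so a stated pair can be checked directly. The pair of 82% and 0.015 is not among them.

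The direction is also unclear. As worded, the null is 90% and the trial would detect acceptability as low as 75%. The success criterion points the other way: it asks whether acceptability reaches 75%, which would normally make 75% the null and 90% the alternative. Both directions therefore need checking.

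At stake is the credibility of the only quantitative justification for the primary endpoint. The synopsis says the findings will lead to an application for a multi-city trial, and readers of that application would take the stated certainty at face value.

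**Working it through.** **Inputs** (all from the synopsis): n = 40 in the intervention arm; acceptability 90% and 75%; one-sided alpha 0.015; stated power 82%. Let X be the number of the 40 who find the intervention acceptable, X ~ Binomial(40, p).

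**1. As worded: null p = 0.90, alternative p = 0.75, reject if X ≤ c.** Alpha = P(X ≤ c | 0.90); power = P(X ≤ c | 0.75).

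| c | alpha | power |
|---|---|---|
| 30 | 0.0051 | 56.0% |
| 31 | 0.0155 | 70.0% |
| 32 | 0.0419 | 81.8% |

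The stated 82% appears at c = 32, where alpha is 0.042. The stated 0.015 appears, to rounding, at c = 31 (0.015495), where power is 70.0%. No row has both.

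**2. Reversed: null p = 0.75, alternative p = 0.90, reject if X ≥ r.** Alpha = P(X ≥ r | 0.75); power = P(X ≥ r | 0.90).

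| r | alpha | power |
|---|---|---|
| 37 | 0.0047 | 42.3% |
| 36 | 0.0160 | 62.9% |
| 35 | 0.0433 | 79.4% |
| 34 | 0.0962 | 90.0% |

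No row has 82% at any alpha, and none has 82% near 0.015.

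**3. Upper bound over all valid tests.** By the Neyman-Pearson lemma, the most powerful test at exactly 0.015 mixes two adjacent cut-offs.
- As worded: weight on c = 31 is (0.015 − 0.00506)/(0.01550 − 0.00506) = 0.953. Power = 0.5605 + 0.953 × (0.7002 − 0.5605) = 69.4%.
- Reversed: weight on r = 36 is (0.015 − 0.00470)/(0.01604 − 0.00470) = 0.908. Power = 0.4231 + 0.908 × (0.6290 − 0.4231) = 61.0%.

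No level-0.015 test with 40 participants can exceed these figures.

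**4. Could an approximation have produced 82%?** z(0.985) = 2.170. Standard errors: √(0.09/40) = 0.0474 at 90% and √(0.1875/40) = 0.0685 at 75%.
- Each hypothesis with its own variance, as worded: (0.15 − 2.170 × 0.0474)/0.0685 = 0.687, power 75.4%.
- The same, reversed: (0.15 − 2.170 × 0.0685)/0.0474 = 0.030, power 51.2%.
- Arcsine, either direction: 64.9%.
- Variance 0.9 × 0.1 used under both hypotheses: 0.15/0.0474 − 2.170 = 0.992, power 83.9%. A noncentral t version of the same formula gives 81.5%.

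Only the last, crude form comes close. Its implied cut-off as worded is 40 × (0.9 − 2.170 × 0.0474) = 31.88, so X ≤ 31, with exact power 70.0%. Reversed it is 40 × (0.75 + 2.170 × 0.0474) = 34.12, so X ≥ 35, with exact alpha 0.043. It may explain where the figure came from, but it does not make it true.

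**5. The rule in the protocol.** Read as an observed proportion, at least 75% means X ≥ 30.
- P(X ≥ 30 | 0.75) = 58.4%.
- P(X ≥ 30 | 0.90) = 99.9%.

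The stated 0.015 and 82% do not describe this rule either.

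**The case against.** The strongest reply is that no test is planned. Acceptability is tabulated and set against a descriptive threshold, then explored in interviews, in a 60-person open-label pilot. Alpha 0.015 governs no decision. This stands, and it limits how serious the point is. A reader might infer that the primary analysis runs at nearly three times its stated type I error; the documents do not support that, because they describe no such test. The protocol does nevertheless publish a power and an alpha, and the pair is wrong.

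A second reply is that the shortfall depends on the method and direction chosen. For its size, this is fair. As worded, the two-variance normal approximation falls about 7 points short of 82%, and the exact cut-off nearest 0.015 falls 12 short. The largest gap, about 40 points, needs both the reversed direction and strict adherence to 0.015 (X ≥ 37, 42.3%). That 82% is unattainable does not depend on the method, because step 3 bounds every valid test.

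Two further readings are tempting. One is that the authors took alpha from the cut-off of 31 and power from the cut-off of 32. Both figures fit to rounding, but only in the direction as worded, and a crude formula with standard deviation 0.3 gives 81% to 84%. With no cut-off or formula in the documents, neither origin is established. The other is that the trial is too small. A test with 82% power at 0.015 would first become possible at 59 intervention participants as worded or 63 reversed, but nothing in the documents requires such a test for this pilot.

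**Conclusion.** The point holds: 82% power at one-sided alpha 0.015, for 90% versus 75% with 40 participants, is not attainable in either direction. At exactly 0.015 the most that can be had is 69.4% as worded or 61.0% reversed. If power near 82% is kept, alpha is about 0.042 (as worded, power 81.8%) or 0.043 (reversed, power 79.4%).

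This assumes a one-sample comparison with a fixed value, independent responses, and all 40 participants answering. Every other input is printed in the synopsis. The cause of the error is not known.

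It should be fixed, but it does not undermine the trial: the planned analysis is a tabulation against a threshold, and no analysis or enrolment figure depends on the wrong pair.

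**What to change.** Keep 40 participants in the intervention arm. In Rationale for Number of Subjects, delete the 82% and the 0.015 and give the operating characteristics of the rule the protocol uses. For example: with 40 participants, an observed proportion of at least 75% (30 or more) will be met with probability 58% if true acceptability is 75%, and 99.9% if it is 90%.

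If a formal test is wanted instead, state one null, one alternative and one exact cut-off, with its own alpha and power. One such rule is 35 or more of 40, with alpha 0.043 against a true 75% and power 79% at a true 90%. That rule requires an observed 87.5%, so it cannot sit beside the present threshold: 32 of 40 (80%) would pass one and fail the other. The threshold wording would then have to change in both synopsis entries (Primary Analysis Plan and Rationale for Number of Subjects), Section 5.1 and Section 10.2.

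The first option costs one or two sentences and a less favourable stated figure; the second also means aligning those four places. Neither changes enrolment or procedures.
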